### **Duration of CHR, MR2, MMR, MR4 and MR4.5**

Duration of Response (DOR) is the time from the date of the first documented molecular (MR2, MMR, MR4, MR4.5) or Hematologic (CHR) response to the date of first documented loss of that response or death due to any cause or progression to AP/BC, whichever occurs first.

The start date is the date of first documented response and the end date is defined as the date of the first documented loss of that response or death due to any cause or progression to AP/BC. Participants continuing without that event will be censored at the date of their last adequate molecular or hematologic response assessment.

DOR for each response level will be analyzed using the Kaplan-Meier Product-Limit method.

Estimates of DOR at specific timepoint and the 25th, median and 75th percentile of the DOR and their 95% confidence intervals will be provided, if applicable.

#### **2.8.1.1 Other secondary efficacy endpoints**

**Progression-Free-Survival (PFS)** is defined as time from the first dose of study medication to disease progression to AP/BC or death due to any cause, whichever occurs first during 24,48 and 72 weeks.

For patients without progression, the patient will be censored at the last molecular assessment date the patient was known to be alive and without progression (on or before the cut-off date).

PFS will be analyzed using the Kaplan-Meier Product-Limit method. Patients who do not progress will be censored at the last adequate assessment. Estimates of the 25th, median and 75th percentile of the PFS and their 95% confidence intervals will be provided, if applicable.

**Overall survival (OS)** is defined as the time from the first dose of study medication to death due to any cause during 24, 48 weeks and 72 weeks during study.

If a patient is not known to have died, then OS will be censored at the latest date the patient was known to be alive (on or before the cut-off date). All deaths will be taken into account whatever the death occurred, i.e., even after interruptions, or discontinuation of study medication due to any reason.

OS will be analyzed using the Kaplan-Meier Product-Limit method. Patients who do not progress will be censored at the last adequate assessment. Estimates of the 25th, median and 75th percentile of the OS and their 95% confidence intervals will be provided, if applicable.

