12.5.2.4 Progression Free Survival

Progression Free Survival (PFS) is defined as time from the first dose of study medication to disease progression to AP/BC or death due to any cause, whichever occurs first, by 24, 48 and 72 weeks.

For patients without progression, the time is censored at the latest date the patient was known to be alive and without progression (on or before the cut-off date).

PFS will be analyzed using the Kaplan-Meier Product-Limit method. Patients who do not progress will be censored at the last adequate assessment. Estimates of the 25th, median and 75th percentile of the PFS and their 95% confidence intervals will be provided, if applicable.

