### **Time to CHR, MR2, MR4, MR4.5 in 72 weeks of therapy**

Time to achieving a response level is defined as the time from the date of the first dose of study medication to the first documented achievement of a response level.

Time to achieve a specific response level will be analyzed using the Kaplan-Meier Product-Limit method. Patients who are known to be without achieving that response level will be censored at the last molecular & hematologic assessment.

The estimated cumulative incidence rates and 95% confidence intervals at 12, 24, 48 and 72 weeks will be presented. The cumulative incidence curve will be plotted. , if applicable. The analyses will be performed using FAS by cohort.

For patients in the FAS who have not experienced any molecular and/or hematologic response, the time will be censored as follows in the Kaplan-Meier analysis:

- If a patient does not achieve the specified response before the cut-off date for the analysis, censoring time will be the last molecular assessment (PCR) date on treatment prior to the cut-off date or the EoT visit, whichever comes first.
- If a patient discontinues study treatment prior to achieving a response for a reason other than disease progression or death, then the patient will be censored at the last molecular assessment (PCR) date on treatment prior to the cut-off date or the EoT visit, whichever comes first.

- If a patient discontinues study treatment prior to achieving a response due to progression or death, then the censoring time will be set to the longest follow-up time in the treatment group, that is, consider the response is impossible to reach.

In case no on-treatment response assessment was performed, the patient will be censored at day 1.

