### **2.8.3 Handling of missing values/censoring/discontinuations**

#### **MMR rates by specific time points:**

Patients without any documented response for which an evaluable response assessment was never provided will be considered as non-responders for the period of time up to that time point.

**Molecular response category by specific time points:** The category “Missing” will be assigned to patients for whom an evaluable response assessment was never provided.

**Time to MMR:** For patients in the FAS who have not experienced any MMR, the time will be censored as follows in the Kaplan-Meier analysis:

If a patient does not achieve the specified response before the cut-off date for the analysis, censoring time will be the last molecular assessment (PCR) date on treatment prior to the cut-off date or the EoT visit, whichever comes first.

If a patient discontinues study treatment prior to achieving a response for a reason other than disease progression or death, then the patient will be censored at the last molecular assessment (PCR) date on treatment prior to the cut-off date or the EoT visit, whichever comes first.

If a patient discontinues study treatment prior to achieving a response due to progression or death, then the censoring time will be set to the longest follow-up time in the treatment group, that is, consider the response is impossible to reach.

In case no on-treatment response assessment was performed, the patient will be censored at day 1.

[figure not shown]
**Duration of MMR:** For patients who have not experienced any event (loss of MMR, progression to AP/BC, or CML-related death), the duration will be censored at the last molecular assessment (PCR) date on treatment.

[figure not shown]
**PFS:** For patients who have not experienced protocol defined event (disease progression to AP/BC or death from any cause), the patients will be censored at the date of last study assessment (PCR, cytogenetic, hematologic or extramedullary) before the cut-off date.

**OS:** Patients who are alive at the time of the analysis data cutoff date will be censored at the date of last contact (see Section 2.1.1) before the cut-off date.

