## 4 Change to protocol specified analyses

No change to the protocol specified analysis has been made.

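### The SAP gives conflicting censoring rules for PFS, one tied to PCR, which does not determine AP/BC, and conflicts with itself on time to CHR; the effect is small and the fix is wording

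*SAP*

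**What the plan says.** **PFS.** SAP 2.8.1.1 defines the event as "disease progression to AP/BC or death due to any cause, whichever occurs first during 24,48 and 72 weeks". For patients without progression it says that "the patient will be censored at the last molecular assessment date the patient was known to be alive and without progression". The next paragraph of the same section adds: "Patients who do not progress will be censored at the last adequate assessment". It does not say which assessment types are adequate.

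SAP 2.8.3, the section on missing values and censoring, says instead that "the patients will be censored at the date of last study assessment (PCR, cytogenetic, hematologic or extramedullary) before the cut-off date".

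Protocol 12.5.2.4 has no molecular restriction: "the time is censored at the latest date the patient was known to be alive and without progression". It too goes on to mention a last adequate assessment. SAP Section 4 states: "No change to the protocol specified analysis has been made".

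**Time to CHR.** The opening text of SAP 2.8.2 on time to response censors non-responders at the last molecular and hematologic assessment. The bullets that follow expressly include patients without a hematologic response. The first two say that "censoring time will be the last molecular assessment (PCR) date on treatment prior to the cut-off date" or the EoT visit, whichever is earlier. The third treats patients who stop for progression or death differently: their censoring time is the longest follow-up in the group.

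**The concern.** A censoring date should be the last time the patient was shown to be free of the event. Protocol 9.1.1 defines accelerated phase and blast crisis by blasts, promyelocytes, basophils and platelets, with no PCR criterion. Protocol 8.4.2 defines CHR by blood counts and absence of extramedullary disease, also without PCR.

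If censoring follows the last PCR while events are taken whenever blood counts show them, the two kinds of patient are treated unequally. An event after the last PCR counts; event-free time after the last PCR does not. The risk set becomes too small and PFS is biased down. By the same mechanism, the cumulative incidence of CHR would be biased up.

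The conflict also matters apart from bias. A programmer working from 2.8.1.1 and a validator working from 2.8.3 could derive different dates for the same patient, and nothing in the SAP says which section governs.

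**Working it through.** **1. The plan's own figure.** The sample size rests on the precision of an AE rate: 1.96² × 0.18 × 0.82 / 0.12² = 39.4, rounded up to 40. Then 40 / 0.9 = 44.4, rounded up to 45, and 45 + 45 + 25 = 115. These match the plan, and none depends on PFS or CHR.

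**2. The PFS rules side by side.**

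| Source | Censoring date | Can it show AP/BC? |
|---|---|---|
| Protocol 12.5.2.4, first rule | latest date known alive and progression-free | yes |
| SAP 2.8.1.1, first rule | last molecular assessment | PCR alone cannot |
| SAP 2.8.1.1, second rule | last adequate assessment, undefined | unclear |
| SAP 2.8.3 | last of four assessment types, PCR included | depends on which is last |

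The first SAP rule is the protocol's rule with a molecular restriction added, and Section 4 does not list it.

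**3. How much follow-up the molecular rule can drop.** PCR is scheduled at Weeks 4, 12, 24, 36, 48, 60 (in-person visits only) and 72 or end of treatment (protocol Table 8-3). Blood counts are taken every 4 weeks from Week 4 to Week 72 (Table 8-6). The longest gap between a blood count and the preceding PCR is:
- with a Week 60 PCR: 20 − 12 = 8 weeks, and likewise at Weeks 32, 44, 56 and 68;
- without it: 68 − 48 = 20 weeks;
- at any visit with a PCR, including end of treatment: 0.

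**4. Size for patients still on study at a cut-off.** Illustration: 45 patients, 4,000 runs, follow-up uniform over 24 to 72 weeks, no Week 60 PCR. Follow-up and event rates are assumptions, not document figures. Mean Kaplan-Meier PFS just before Week 48:

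| Assumed annual event rate | Protocol rule | Last 4-weekly visit | Last PCR | Protocol minus PCR |
|---|---|---|---|---|
| 5% | 95.4% | 95.2% | 94.9% | 0.5 points |
| 10% | 90.7% | 90.4% | 89.8% | 0.9 points |
| 20% | 81.4% | 80.9% | 79.7% | 1.7 points |

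**5. Size for early leavers.** Illustration: 6% progression and 40% discontinuation by Week 72 (both assumed), no Week 60 PCR. Under the 4-weekly blood-count rule, early leavers are censored about 13 days before leaving and the Week 72 event probability is 6.04%. Under the PCR rule:

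| Early leavers with an end-of-treatment PCR | Mean time lost | Week 72 event probability |
|---|---|---|
| 0% | 48 days | 6.28% |
| 80% | 10 days | 6.09% |
| 100% | 0 days | 6.04% |

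The largest difference is 6.28 − 6.04 = 0.24 points. A 95% half-width for a 6% rate in 45 patients is 1.96 × √(0.06 × 0.94 / 45) = 0.069, about 7 points.

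**6. Time to CHR.** SAP Table 2-2 places hematologic response at Weeks 12, 24, 36, 48 and 72, all of which are PCR weeks. Moving from the PCR date to the hematologic response date should therefore shift few censoring times. This effect was not simulated.

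**The case against.** The strongest reply is that the conflict comes down to one stray word. SAP 2.8.3 already admits hematologic and extramedullary assessments, and the last-adequate-assessment sentence comes from the protocol and can be read consistently with 2.8.3. PCR is scheduled at end of treatment, and protocol Section 8 asks for all final-visit assessments in anyone who stops early. The analysis is descriptive. All of this stands, and it limits the size; it does not remove the conflicting text.

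A reader might infer more than the documents support:

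- **That PFS is simply censored at the last PCR.** That is one of the SAP's rules, and 2.8.3 says otherwise.
- **That early leavers lose about seven weeks of follow-up.** The 48 days arise only if no early leaver has the scheduled end-of-treatment PCR and nobody has a Week 60 PCR.
- **That PFS collapses after Week 48.** Read just before Week 72, the first illustration at a 5% annual rate gives 73.6% under the PCR rule against 93.1% under the protocol rule. This follows from its set-up: no event-free patient has a PCR after Week 48, so from then on only patients with events remain at risk. The protocol schedules PCR at in-person Week 60 visits, at Week 72 and at end of treatment.
- **That AP/BC and CHR are formally assessed every 4 weeks.** Only blood counts are. Hematologic response and progression status are scheduled no more often than PCR. After Week 4, physical examination may be omitted except at Weeks 12, 24, 36, 48 and 72.
- **That time to CHR is plainly PCR-censored.** The lead sentence names hematologic assessment too, and the third bullet handles progression and death separately. Under protocol 9.1.1, absence of CHR at three months or later is treatment failure requiring discontinuation, so the long gap after Week 48 should rarely apply to CHR non-responders.

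**Conclusion.** The inconsistency is real and should be resolved. SAP 2.8.1.1 and 2.8.3 give different PFS censoring dates, the molecular rule departs from protocol 12.5.2.4 without being declared, and PCR does not determine the event. SAP 2.8.2 also contradicts itself on time to CHR.

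The consequence is small. Lost PFS follow-up is zero when the last visit has a PCR. Otherwise it is at most 8 weeks per patient on the scheduled visits, or at most 20 weeks after Week 48 if Week 60 is remote. Under the assumed rates, PFS just before Week 48 falls by about 0.5 to 1.7 points at an interim look, and the Week 72 event probability rises by at most about 0.2 points through early leavers. The rule matters mainly at interim cut-offs and for patients without an end-of-treatment PCR. The effect on time to CHR is likely very small. No hypothesis test, sample size or primary safety conclusion is affected.

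**What to change.** - State one PFS censoring rule in identical words in SAP 2.8.1.1 and 2.8.3. Use either the protocol's latest date known alive and progression-free, or the last assessment able to show AP/BC (hematologic or extramedullary). Under the second option, PCR should not qualify on its own.
- Delete the molecular restriction from 2.8.1.1, and remove or define the last-adequate-assessment sentence.
- In SAP 2.8.2, censor time to CHR at the last hematologic response assessment, and keep the existing bullet on progression and death.
- Keep PCR-based censoring for MR2, MMR, MR4 and MR4.5.
- List any remaining departure from protocol 12.5.2.4 in SAP Section 4.

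The cost is SAP wording only, with no new data, visits or patients.

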**Table 2-5 Last contact date data sources**

Source data	Conditions
Date of random allocation	No condition
Last contact date/last date patient was known to be alive from Survival Follow-up page	Patient status is reported to be alive, lost to follow-up or unknown
Start/End dates from further antineoplastic therapy	Non-missing medication/procedure term
Start/End dates from drug administration record	Non-missing dose. Doses of 0 are allowed
End of treatment date from end of treatment page	No condition
Any specific efficacy (molecular or cytogenetic) assessment date if available	Evaluation is marked as 'done'
Laboratory/█ collection dates	Sample collection marked as 'done'
Vital signs date	At least one non-missing parameter value
Performance status date	Non-missing performance status
Start/End dates of AE	Non-missing verbatim term

The last contact date is defined as the latest complete date from the above list on or before the respective data cut-off date. The cut-off date will not be used for last contact date unless the patient was seen or contacted on that date. No date post cut-off date will be used. Completely imputed dates (e.g., the analysis data cut-off date programmatically imputed to replace the missing end date of a dose administration record) will not be used to derive the last contact date.

The last contact date will be used for censoring of patients in the analysis of overall survival.

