## **3 Sample size calculation**

This is an open label, three-cohort study to assess safety and efficacy of study of asciminib (ABL001) monotherapy in patients with chronic myeloid leukemia in chronic phase (CML-CP) previously treated with at least 2 prior TKIs (tyrosine kinase inhibitors) and CML-CP patients harboring the T315I mutation previously treated with at least 1 prior TKIs.

For all CML-CP with the exception of those harboring the T315I mutation, there will be random allocation of patients to eliminate selection bias at the time of cohort allocation. Those patients will be assigned to either Cohort A consisting of asciminib 40 mg BID patients or Cohort B consisting of asciminib 80 mg QD. For CML-CP patients harboring the T315I mutation, they will be assigned to Cohort C with asciminib 200 mg BID, which is the dose required for that patient population. It is worthwhile mentioning that random allocation of patients in cohorts A and B will be pursued for patient selection only. The study is not powered to show differences in Primary and Secondary endpoints between study cohorts.

Primary objective of the study is to assess safety profile of this combination drug during 24 weeks for all cohort patients.

A sample size of 40 evaluable patients for Cohort A is estimated based on a two- sided 95% confidence interval for an incidence rate of an AE using the large sample normal approximation that will extend 0.12 from the observed incidence rate of an AE (precision or margin of error of 12%) for an expected incidence rate of 18%. Considering drop-out rate of 10%, approximately 45 patients will be enrolled for safety assessment for the Cohort A of this study.

Retaining the same assumptions, approximately 45 patients will also be enrolled for Cohort B. Additionally for Cohort C, approximately 25 patients will be enrolled.

Thus, approximately total 115 (45+45+25=115) patients will be enrolled for Cohort A (n1=45) and Cohort B (n2=45) and for Cohort C (n3=25) of the study.

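### SAP 2.8.1.1 and protocol 12.5.2.5 each give two contradictory censoring rules for overall survival; the one that turns on progression should be deleted

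*SAP*

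**What the plan says.** SAP 2.8.1.1 defines OS as "time from the first dose of study medication to death due to any cause during 24, 48 weeks and 72 weeks". Its rule for anyone without a recorded death is: "then OS will be censored at the latest date the patient was known to be alive". That date may not fall after the cut-off. The section adds: "All deaths will be taken into account whatever the death occurred".

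The next paragraph of the same section reads: "OS will be analyzed using the Kaplan-Meier Product-Limit method. Patients who do not progress will be censored at the last adequate assessment". A few lines earlier the PFS text reads: "PFS will be analyzed using the Kaplan-Meier Product-Limit method. Patients who do not progress will be censored at the last adequate assessment". The two differ only in the endpoint name.

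Two other places in the SAP deal with OS censoring. Section 2.8.3 says: "Patients who are alive at the time of the analysis data cutoff date will be censored at the date of last contact". Section 2.1.1, below Table 2-5, says: "The last contact date will be used for censoring of patients in the analysis of overall survival".

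Protocol 12.5.2.5 has the same pair of paragraphs, including the sentence on patients who do not progress.

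**The concern.** Progression is no part of the OS definition, so it should not decide who is censored. The sentence makes no exception for patients who have died. Taken at its word, someone who dies without progressing is censored at an assessment before the death, and the death never enters the curve. A living patient without progression is cut back from last contact to last assessment.

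Two censoring rules for one endpoint also leave the choice to whoever programs the analysis. Going back to the protocol does not settle it. The SAP introduction says its methods follow the protocol unless otherwise specified, SAP Section 4 declares no change from it, and the protocol contains the same conflict. Neither document says which rule prevails, or what counts as an adequate assessment for OS.

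**Working it through.** The documents state no OS figure (no assumed death rate, event count or power for OS), so there is nothing to reproduce. The check is a comparison of the rules, followed by an illustration.

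**1. Where each rule stands**

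| Place | Who is censored for OS | At what date |
|---|---|---|
| SAP 2.8.1.1 and protocol 12.5.2.5, OS definition and the text after it | patients not known to have died | latest date known alive |
| SAP 2.8.3, OS | patients alive at cut-off | last contact |
| SAP 2.1.1, Table 2-5 | patients not known to have died at cut-off | last contact |
| SAP 2.8.1.1 and protocol 12.5.2.5, Kaplan-Meier paragraph | patients who do not progress | last adequate assessment |

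The first three agree. The fourth does not.

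**2. Which patients the rules treat differently**

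| Patient | Last-contact rule | Progression sentence, taken literally |
|---|---|---|
| Died after progression | event | event |
| Died without progression | event | censored before death |
| Alive, no progression | censored at last contact | censored at last adequate assessment |
| Alive after progression | censored at last contact | not addressed |

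The second row biases OS upward. Which deaths fall in it depends on the meaning of progression. PFS uses progression to AP/BC; protocol 9.1.1 also classes CML-related death as progression. On the wider meaning, only deaths that are neither CML-related nor preceded by AP/BC are lost.

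The third row discards known-alive time, because Table 2-5 draws on survival follow-up, adverse event, dosing and later-therapy dates as well as response assessments. Fewer patients at risk would also give any death still counted more weight. I have not put a number on this, since the documents do not give the gap between last assessment and last contact.

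**3. Illustration**

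Inputs: cohort sizes of 45 (A and B) and 25 (C) from SAP Section 3. The numbers of deaths are assumed. Nobody else is censored before week 72.

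*All deaths without progression, n = 45.* OS counting every death is 1 − d/45:
- d = 1: 44/45 = 97.8%
- d = 2: 43/45 = 95.6%
- d = 3: 42/45 = 93.3%

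Under the progression sentence no event is left, so the curve reads 100% each time.

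*Only some deaths without progression.* Deaths are spaced evenly over 72 weeks. The earlier ones are those without progression, each censored 4 weeks before it occurred.

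| n | Deaths | Without progression | All deaths counted | Progression sentence |
|---|---|---|---|---|
| 45 | 2 | 1 | 43/45 = 95.6% | 43/44 = 97.7% |
| 45 | 4 | 2 | 41/45 = 91.1% | 41/43 = 95.3% |
| 45 | 4 | 3 | 41/45 = 91.1% | 41/42 = 97.6% |
| 25 | 4 | 2 | 21/25 = 84.0% | 21/23 = 91.3% |
| 25 | 4 | 3 | 21/25 = 84.0% | 21/22 = 95.5% |

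**4. What the documents offer on death rates**

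Protocol 1.1.2.2 reports deaths leading to treatment discontinuation in 3 of 239 phase I patients: two ALL patients with progressive disease, and one patient with aspiration pneumonia after a bypass procedure. Scaled to 45 patients, that is 45 × 3/239 = 0.6 deaths, of which 45 × 1/239 = 0.2 without progression. This is not an OS rate: it leaves out other deaths, mixes diseases and has different follow-up. The 5-year survival of 80% to 95% in protocol 1.1.1 describes TKI therapy for CML in general, not this pretreated population.

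**The case against.** The strongest reply is that the plan already has the right rule, several times over. To lose a death, a programmer would have to set aside the endpoint definition, the explicit statement that all deaths count, the section devoted to censoring and the last-contact definition, all in favour of one stray sentence. That is improbable, and this part of the reply stands.

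It can also be said that the sentence is only loose shorthand for patients without the event. Even in the PFS paragraph, its literal wording would censor deaths without progression, against the PFS definition. That is a fair reading, but it does not remove the conflict: the sentence still gives the last adequate assessment as the OS censoring date, where the other rules give last contact.

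Little rests on the result. OS is one of many secondary, descriptive endpoints, no hypothesis is tested (SAP 2.8.4), and the study is not powered to compare cohorts. SAP 2.6.3 has deaths summarised and all of them listed, so a death missing from the OS curve would still appear in the report. This limits the consequence. It does not make two incompatible rules acceptable in a prespecified plan.

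**Conclusion.** The point holds as an internal contradiction in the OS censoring rules, present in both documents and probably caused by text carried over from PFS. If the progression sentence were applied, deaths without progression would be lost and OS biased upward, and living patients without progression would lose follow-up. The only sizes available are illustrative. With 1 to 3 such deaths among 45 patients, no other deaths and no other early censoring, 72-week OS would read 100% instead of 97.8% to 93.3%. The effect is smaller where some deaths follow progression, and larger for a given number of deaths in the cohort of 25.

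A reader might infer two stronger things that the documents do not support:
- **That the plan's OS analysis excludes deaths without progression.** It does not follow, because the definition, SAP 2.8.3 and SAP 2.1.1 point the other way and would probably be followed.
- **That such deaths are to be expected here, so a visible bias is likely.** The documents give no OS or death rate for this population and no split of deaths by progression. The phase I count is too narrow to supply one and, for what it is worth, scales to fewer deaths than the illustration assumes.

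In practice the importance is modest, but the text is wrong as written and easily put right.

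**What to change.** Delete the sentence about patients who do not progress from the OS paragraph in SAP 2.8.1.1 and in protocol 12.5.2.5; the PFS paragraph is not touched by this change. Keep one OS rule: every death is an event, and patients not known to have died are censored at the last contact date (SAP 2.1.1) on or before the cut-off, as SAP 2.8.3 already provides.

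The cost is one sentence removed from each document. No new data, method or sample size is involved.
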